10.5.2 Barnes Akathisia Rating Scale (BARS)

Descriptive statistics for BARS total score at baseline and changes from baseline at each assessment visit (including the end of the Open-label Treatment Period) will be presented for the Safety Population.

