7.8.3 Rescue Medications

Medications for the acute treatment of extrapyramidal symptoms and akathisia are allowed.

Zolpidem may be taken for insomnia, in the evening at bedtime and prior to midnight for the treatment of insomnia. If zolpidem is not available in specific regions, another sedative hypnotic may be approved by the Sponsor or designee.

The date of each dose of rescue medication administration as well as the name and dosage regimen of the rescue medication must be recorded on the eCRF.

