8.2.7.2.2 Barnes Akathisia Rating Scale

The BARS is a rating scale for drug-induced akathisia developed by Barnes (1989). It includes the rating of observable restless movements, the subjective awareness of restlessness, and the distress associated with the akathisia. There is also a global rating for severity. The scale is completed by the investigator or an expert site-based rater after a standard examination. Objective akathisia, subjective awareness and subjective distress are rated on a 4-point scale from 0 to 3, yielding a total score from 0 to 9. The Global Clinical Assessment of Akathisia is rated separately, on a 6-point scale from 0 to 5. The BARS is to be completed at Screening/Baseline (Visit 1/Day 1) and Visits 2, 5, 7, 9, 11, 13, 15, and 16/ET as specified in the Schedule of Evaluations (Table 1-1).

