9.4.5.5 Other Safety Parameters

Descriptive statistics for change from baseline to assessment visit and to the end of the Open-label Treatment Period in AIMS total score, BARS total score, and SAS total score will be summarized based on the Safety Population.

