15.2 Repeated or Unscheduled Assessments of Safety Parameters

For visits with repeated or unscheduled assessments of laboratory parameters, the non-missing values of the scheduled assessment will be used for summary statistics. If the scheduled assessments are missing, the last value from repeated or unscheduled assessments within the analysis window will be used for the visit. If repeated or unscheduled AIMS, BARS, SAS, vital signs or ECGs occur, apply the time-window rule and select the last non-missing values for each visit or endpoint.

All assessments during the Open-label Treatment Period will be included in PCS value determination and will be presented in the data listings.

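### The BARS global akathisia rating is collected at nine visits but enters no planned summary, and no planned output counts patients with new or worse akathisia on examination

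*SAP*

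**What the plan says.** Protocol 8.2.7.2.2 defines two BARS results. The first is a total: "Objective akathisia, subjective awareness and subjective distress are rated on a 4-point scale from 0 to 3, yielding a total score from 0 to 9". A second result stands apart from it: "The Global Clinical Assessment of Akathisia is rated separately, on a 6-point scale from 0 to 5". Both come from the same examination, on this schedule: "The BARS is to be completed at Screening/Baseline (Visit 1/Day 1) and Visits 2, 5, 7, 9, 11, 13, 15, and 16/ET".

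The analysis sections use only the first. Protocol 9.4.5.5 plans descriptive statistics for change in the three extrapyramidal scales: "AIMS total score, BARS total score, and SAS total score will be summarized". SAP 10.5.2 follows it: "Descriptive statistics for BARS total score at baseline and changes from baseline at each assessment visit". End of open-label treatment counts among those visits. The SAP does not mention the global rating. Protocol 9.1 defines descriptive statistics for a continuous variable as the number of patients, mean, SD, median, minimum and maximum.

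One general sentence in SAP 15.2 may reach the global rating: "All assessments during the Open-label Treatment Period will be included in PCS value determination and will be presented in the data listings".

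Akathisia also appears as an adverse-event term. It is in the narrow extrapyramidal list (SAP Table 10-1), and SAP 10.1 tabulates treatment-emergent events by preferred term and severity.

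**The concern.** Safety and tolerability is the primary objective, and the plan treats akathisia as a harm to watch. It has its own scale, it is in the narrow extrapyramidal term list, and the protocol provides for its treatment ("Medications for the acute treatment of extrapyramidal symptoms and akathisia are allowed", cited here only as context).

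For an uncommon harm, the useful results are how many patients developed it or got worse, and how severe it became. The BARS global rating is the scale's overall severity grade and suits that purpose. Under the plan it enters no table, and the total score is reduced to a distribution of changes at each visit. The report would then have no patient count for akathisia found on examination.

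The SAP does give patient counts elsewhere. Laboratory values, vital signs and ECGs get counts of patients meeting criteria for potentially clinically significant (PCS) values. Laboratory parameters also get shift tables. The C-SSRS, which is also an ordinal rating, gets worst-category distributions and counts of emergence and worsening.

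**Working it through.** 1. **Is the global rating inside the total?** Protocol 8.2.7.2.2 gives three items, each with a maximum of 3. The largest total is 3 × 3 = 9, which reproduces the stated 0 to 9 range. Adding the global rating would give 9 + 5 = 14. The global rating is therefore not part of the total, and a summary of the total does not report it.

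2. **How often is it rated?** The text lists Visits 1, 2, 5, 7, 9, 11, 13, 15 and 16/ET, which is nine. The AIMS/BARS/SAS row of Protocol Table 1-1 marks the same nine. Visit 1/Day 1 is the last double-blind visit of the lead-in study (Visit 8/Day 43) and comes before open-label dosing, so eight ratings fall after dosing starts. With about 760 patients planned, the most that scheduled visits can yield is 8 × 760 = 6,080 open-label ratings. Dropout will lower this.

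3. **What can the planned total-score summary show?** The documents give no akathisia rate, so the inputs below are assumptions. Suppose *k* of 760 patients have a change of +4 at a given visit and the others change by *d* on average. The mean change is [4*k* + *d*(760 − *k*)]/760.
   - *k* = 15 (15/760 = 2.0%), *d* = −0.05: (60 − 37.25)/760 = +0.03.
   - *k* = 15, *d* = 0: 60/760 = +0.08.
   - *k* = 38 (5% of 760, the SAP's threshold for a common event), *d* = −0.05: (152 − 36.1)/760 = +0.15.
   - *k* = 38, *d* = 0: 152/760 = +0.20.

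   On a 0 to 9 scale all four means are small, and the median is 0 if most patients do not change. The maximum would be at least +4 in every case, so it cannot tell 15 patients from 38. If patients worsen at different visits, each visit's mean is smaller still, and by-visit summaries do not add up to a number of distinct patients.

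4. **Does another planned output supply the count?**
   - *Listings (SAP 15.2).* The sentence joins listings to PCS determination. SAP Tables 10-2, 10-4 and 10-5 set PCS criteria for laboratory values, vital signs and ECGs, not for the BARS. The ratings may be listed, but a listing is not a summary.
   - *Adverse events.* Patients are questioned in a non-leading way (Protocol 8.2.1.4), and no section ties a BARS rating to the recording of an event. The event table and the examination can therefore give different numbers.

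**The case against.** The strongest case on the other side has four parts.

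- **A reader might infer that akathisia severity would go unreported, or that the ratings would never be seen.** The documents do not support this. SAP 15.2 may place every open-label assessment in listings. Akathisia is a named preferred term, the investigator grades each event mild, moderate or severe (Protocol 8.2.1.3.1), and events are tabulated by severity. An adverse event can also be a sign (Protocol 8.2.1.1), so nothing prevents akathisia found on examination from being recorded as one. This part stands. What is missing is narrower: a summary of the global rating and a patient count from the examination.

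- **A reader might infer that patients who worsen would be invisible without a table of the global rating.** That is too strong. The planned maximum and SD would register large changes in the total, and the total itself includes an observer-rated item. The signal could be noticed. The number of patients behind it could not be read off.

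- **A reader might infer that the SAP departs from the protocol.** It does not. Protocol 9.4.5.5 has the same limit, and AIMS, BARS and SAS are treated alike. The study is single-arm and descriptive, and neither document promises a categorical BARS output. This stands, and it makes the point one of analysis choice. The choice still leaves collected safety data unsummarised under the primary objective.

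- **Baseline.** The SAP baseline is the last value before double-blind dosing in the lead-in study. A shift from it would mix lead-in change with open-label change and needs a lead-in global rating, which these documents do not show. This stands, and the fix allows for it.

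**Conclusion.** The point holds as a reporting gap. The BARS global rating is in no planned summary, and no planned output counts patients with new or worse akathisia on examination. Up to 6,080 open-label ratings are affected if all 760 patients attend all eight scheduled visits. In the illustration, 15 to 38 worsening patients (2% to 5%) move the mean total by +0.03 to +0.20. Those effect sizes are assumed and predict nothing about this trial. They show only that the planned mean and median can stay near zero while the maximum gives no count.

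Adverse-event tables and possible listings reduce the loss but do not remove it. No sample-size, power or error-rate figure depends on this, because the sample size is not power-based. The change is worth making before the tables are final, but the gap does not invalidate the study.

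**What to change.** Keep the total-score summary and add to SAP 10.5.2:

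1. The number and percentage of patients in each global category (0 to 5) at baseline, at each scheduled BARS visit and at the end of the Open-label Treatment Period.
2. A shift table from the baseline category to the worst category at any open-label assessment, unscheduled ones included. SAP 15.2 keeps the last value in a window for by-visit summaries, which could drop the worst one. Give the percentage of patients worse than baseline, among those with a baseline and at least one open-label rating.
3. The same shift twice: from the SAP baseline, and from the Visit 1/Day 1 rating, so that open-label change can be told apart from lead-in change.

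The shift from Visit 1/Day 1 uses ratings on this study's own schedule. The shift from the SAP baseline assumes that the lead-in studies recorded the global rating, which should be confirmed. If the sponsor prefers listings only, SAP 10.5.2 should say so and give the reason, though that would leave the count missing.

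The cost is SAP wording and one or two extra tables. This study needs no new data collection, and no clinical rule changes.

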10.5.3 Simpson-Angus Rating Scale (SAS)

Descriptive statistics for SAS total score at baseline and changes from baseline at each assessment visit (including the end of the Open-label Treatment Period) will be presented for the Safety Population.

10.5.4 Columbia-Suicide Severity Rating Scale (C-SSRS)

The number and percentage of patients with suicidal ideation or suicidal behavior as recorded on the C-SSRS will be tabulated for lifetime history (assessed at the enrollment of lead-in studies), baseline, Open-label Treatment Period, and Safety Follow-up for the Safety Population. Baseline of C-SSRS for each patient is defined as the last non-missing 'since last visit' assessment before the first dose of study treatment during the lead-in studies. The distribution of responses for the most severe suicidal ideation and most severe suicidal behavior will be presented.

The severity of suicidal ideation will be presented in the following order:

- Wish to be dead
- Non-specific active suicidal thoughts
- Active suicidal ideation with any methods (not plan) without intent to act
- Active suicidal ideation with some intent to act, without specific plan
- Active suicidal ideation with specific plan and intent

The severity of suicidal behavior will be presented in the following order:

- Preparatory acts or behavior
- Aborted attempt
- Interrupted attempt

Confidential Page 25 of 40

- Actual attempt
- Completed Suicide (for Open-label Treatment Period and for Safety Follow-up only)

For each analysis period (lifetime, baseline, Open-label Treatment Period, and safety follow-up), each patient will be counted only once for suicidal ideation and for suicidal behavior, based on the most severe suicidal ideation and the most severe suicidal behavior reported during each specific period. A listing of patients with suicidal ideation or suicidal behavior will be provided. A listing of all AEs for patients with suicidal ideation or suicidal behavior will also be provided.

In addition, the number and percentage of patients with the following emergence of suicidal ideation or of suicidal behavior during the Open-label Treatment Period will be tabulated for the Safety Population:

- Emergence of suicidal ideation (no suicidal ideation at Baseline, and any type of suicidal ideation during Open-label Treatment Period)
- Emergence of serious suicidal ideation (no suicidal ideation at Baseline, and any serious suicidal ideation [Active suicidal ideation with specific plan and intent, or Active suicidal ideation with some intent to act, without specific plan] during Open-label Treatment Period)
- Worsening of suicidal ideation (most severe suicidal ideation during Open-label Treatment Period was more severe than it was at Baseline)
- Emergence of suicidal behavior (no suicidal behavior at Baseline, and any type of suicidal behavior during Open-label Treatment Period).

Confidential Page 26 of 40

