6.4 Stopping Criteria

6.4.1 Discontinuation of Patients from Therapy or Assessment: Patient-level Stopping Criteria

A premature discontinuation will occur when a patient who signed the ICF ceases participation in the study, regardless of circumstances, before the completion of all study visits and procedures. Patients can be prematurely discontinued from the study for one of the following reasons:

- Death
- AE
- Lack of efficacy (patients whose MDD symptoms worsen or are determined by the Investigator to not be adequately controlled prior to completing the open-label treatment period may be withdrawn from the study to start appropriate treatment at the Investigator's discretion)
- Protocol violation
- Study terminated by Sponsor
- Site terminated by Sponsor
- Withdrawal by subject or withdrawal of consent
- Lost to follow-up
- Pregnancy
- Other

NOTE: If a patient discontinues due to withdrawal of consent and either a concurrent AE was reported or concurrent lack of efficacy was documented, the study site should query and confirm the primary reason for discontinuation and record the primary reason for discontinuation on the electronic case report form (eCRF).

Patients who discontinue from the study, including patients who discontinue due to lost to follow-up, and do not return to the study center for final assessments must be requested in writing to return to the study center for a final assessment. A copy of the letter, together with the source documentation, will be kept in the Investigator's files. The reason for premature discontinuation from the study will be recorded on the Study Termination Page of the eCRF. Study center staff may be contacted by the Sponsor after each premature discontinuation to ensure that proper characterization of the reason for discontinuation is captured.

All patients who prematurely discontinue from the study regardless of cause should be seen for final assessments at an ET Visit. All patients who prematurely discontinue from the study should return for the Safety Follow-up Visit.

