8.2.7 Other Safety Assessments

8.2.7.1 Columbia-Suicide Severity Rating Scale

The C-SSRS is a clinician-rated instrument that reports the severity of both suicidal ideation and behavior (Posner et al, 2011). The C-SSRS will be completed by a trained and Sponsor-approved rater.

Suicidal ideation is classified on a 5-item scale:

- 1. Wish to be dead
- 2. Nonspecific active suicidal thoughts
- 3. Active suicidal ideation with any methods [not plan] without intent to act
- 4. Active suicidal ideation with some intent to act, without specific plan, and
- 5. Active suicidal ideation with specific plan and intent.

The C-SSRS also captures information about the intensity of ideation, specifically the frequency, duration, controllability, deterrents, and reasons for the most severe types of ideation.

Suicidal behavior categories are:

- Completed suicide
- Actual attempt
- Interrupted attempt
- Aborted attempt, and
- Preparatory acts or behavior

More than 1 classification can be selected provided it represents separate episodes. For actual attempts only, the actual or potential lethality is classified for the initial, most lethal, and most recent attempts.

The C-SSRS will be completed at all study visits. At Screening/Baseline (Visit 1/Day 1) and at all other visits, the C-SSRS will be completed for suicidal ideation and behavior since the previous visit ("Since Last Visit" version). Before the patient leaves the study site, the Investigator or appropriately qualified designee will assess the patient's C-SSRS results.

The patient should not be released from the study center until the results of the C-SSRS are reviewed and the patient is not considered to be at risk. If there is doubt about whether a patient is at risk, the Investigator must obtain appropriate psychiatric consultation. The results of the C-SSRS will be recorded in the eCRF. The C-SSRS will be completed by a trained and Sponsor-approved rater.

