9.4.5.5.1 Columbia Suicide Severity Rating Scale (C-SSRS)

The number and percentage of patients with suicidality as measured by the C-SSRS will be summarized for the Open-label Treatment Period, where suicidality was defined as having at least one occurrence of suicidal ideation or at least one occurrence of suicidal behavior.

The distribution of responses for the most severe suicidal ideation and the most severe suicidal behavior will be summarized for lifetime history.

The distribution of responses for the most severe suicidal ideation and the most severe suicidal behavior at baseline and during the Open-label Treatment Period will be summarized.

Emergence of suicidal ideation, serious suicidal ideation, suicidal behavior, and worsening of suicidal ideation (ie, compared with the first dose of study treatment from the lead-in study) during the Open-label Treatment Period will be summarized.

The details of analyses of C-SSRS will be provided in the SAP.

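### The suicidal-behaviour tables draw on C-SSRS forms alone, so a suicide or attempt known only from AE, SAE or death reports can be missing from them

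*SAP*

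**What the plan says.** **Source of the tables.** SAP 10.5.4: "The number and percentage of patients with suicidal ideation or suicidal behavior as recorded on the C-SSRS will be tabulated". The periods are lifetime history, baseline, Open-label Treatment Period and Safety Follow-up, in the Safety Population. Protocol 9.4.5.5.1 has the same source: "The number and percentage of patients with suicidality as measured by the C-SSRS will be summarized for the Open-label Treatment Period".

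**Counting rule.** Each patient counts once per period, "based on the most severe suicidal ideation and the most severe suicidal behavior reported during each specific period". The severity order for behaviour ends with the row "Completed Suicide (for Open-label Treatment Period and for Safety Follow-up only". A further row counts emergence of suicidal behaviour during open-label treatment in patients with none at baseline.

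**When the form is filled.** Protocol 8.2.7.1: "The C-SSRS will be completed at all study visits". At each visit "the C-SSRS will be completed for suicidal ideation and behavior since the previous visit".

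**Patients who leave.** Protocol 6.4.1 says that all early discontinuers should attend an Early Termination (ET) visit and a Safety Follow-up visit. Both carry a C-SSRS in Table 1-1. The section also foresees non-attendance: "Patients who discontinue from the study, including patients who discontinue due to lost to follow-up, and do not return to the study center" must be asked in writing to come back.

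**AE and SAE data.** Protocol 8.2.1.4 has SAEs reported from consent to 30 days after the last known dose, whether or not a visit takes place. SAP 10.1 does not count as treatment-emergent any AE occurring more than 1 day after the last open-label dose. It tabulates SAEs for the Open-label Treatment Period and lists SAEs, AEs leading to withdrawal, and deaths.

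**Linked listing.** SAP 10.5.4: "A listing of all AEs for patients with suicidal ideation or suicidal behavior will also be provided".

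**The concern.** A form that looks back from a visit can record an act only if a form is completed after the act. Some severe acts plausibly end attendance, and a suicide always does. If the C-SSRS is the only source, those acts are the ones most exposed to being missed, and the error can only lower the count.

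The study's primary objective is safety and tolerability in MDD, and suicidality is a named safety summary. At stake is whether the study report could show no completed suicide, or too few patients with suicidal behaviour, in the tables a reader would turn to first, while the SAE or death listing in the same report shows the event.

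**Working it through.** The plan gives no suicidality rate, power or precision, so there is no figure of its own to reproduce. The check is mainly one of reading; the arithmetic only gives scale.

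**Step 1: can an act go without a later form?**

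| Situation | Later scheduled C-SSRS? |
|---|---|
| Attempt, patient attends the next visit | Yes |
| Attempt, patient discontinues but attends ET or Safety Follow-up | Yes |
| Attempt, patient attends neither | No |
| Suicide between visits | No visit is possible, and nothing requires a form after a death |

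The gap is confined to the last two rows. In the second row, an open-label attempt first captured at Visit 17, because ET was missed, could be assigned to Safety Follow-up; SAP 10.5.4 does not say which period it belongs to.

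**Step 2: does another source fill the table?** SAP 10.5.4 names no other source for the behaviour categories, the completed-suicide row or the emergence row. It sets no denominator beyond the Safety Population and does not say how patients with no later form are handled. By contrast, SAP 10.2 to 10.4 do restrict PCS percentages to patients with a baseline value and at least one later assessment.

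**Step 3: do the AE tables cover the gap?** Partly.
- During open-label treatment the event appears by preferred term in the TEAE and SAE tables. Suicide-related terms are not grouped, whereas SAP Table 10-1 groups extrapyramidal terms in addition to the rating scales.
- In follow-up, an act more than 1 day after the last dose is not a TEAE, and the SAE table stops with open-label treatment. SAP 10.5.4 is then the only incidence table. Without a later C-SSRS the act appears in listings only.
- SAE reporting runs to 30 days after the last dose, while Visit 17 falls about 14 days after it (Day 197 against Day 183). About 30 − 14 = 16 days of SAE reporting thus lie beyond the last scheduled form, even for completers.

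**Step 4: scale.** Input: N = 760 planned (protocol synopsis). Intervals are exact (Clopper-Pearson) 95%.
- One missed patient: 1/760 = 0.13 percentage points.
- True count 1, missed: the table shows 0/760 (0 to 0.48%) instead of 1/760 = 0.13% (0.003% to 0.73%).
- True count 3, one missed: 2/760 = 0.26% instead of 3/760 = 0.39%.

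**Step 5: chance of at least one missed patient.** Formula: 1 − (1 − p·m)^760, where p is the true proportion with suicidal behaviour and m the share with no later form. Both are assumptions; the documents give neither.

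| p | m = 10% | m = 25% | m = 50% |
|---|---|---|---|
| 0.1% | 0.073 | 0.173 | 0.316 |
| 0.3% | 0.204 | 0.435 | 0.680 |
| 0.5% | 0.316 | 0.613 | 0.851 |
| 1% | 0.533 | 0.851 | 0.978 |

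The spread, 7% to 98%, shows that the inputs decide the answer.

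**The case against.** The strongest reply is that a section headed C-SSRS properly reports the instrument on its own data, with AEs, SAEs and deaths reported separately, and that a combined count is a new summary and not the correction of an error. That is a coherent way to report. It stands as a reason to keep the C-SSRS-only table, but it does not explain how the completed-suicide row is filled, or where an act in follow-up is counted.

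Three stronger readings are tempting, and the documents do not support them.

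- *A patient with no later form is scored as having no suicidal behaviour.* No such rule exists. The SAP is silent and could be applied with these patients treated as missing. Only with the whole Safety Population as denominator does omission have the same effect.
- *The completed-suicide row can never be filled.* The C-SSRS is clinician-rated and has that category, the SAP plans the row for both on-study periods, and protocol 8.4 allows unscheduled visits for repeat assessments. A rater could complete a form after a death. The point is only that nothing requires it.
- *The event is lost, or every early exit escapes the C-SSRS.* SAE reporting does not depend on visits, and SAE and death listings are planned. Discontinued patients should attend two further visits with a C-SSRS, non-returners are recalled in writing, and remote C-SSRS assessment is permitted during open-label treatment (Table 1-1 footnote).

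The SAP also does not restate the C-SSRS as the selector for the linked AE listing. That it would miss the same patients is an inference from its place in the section.

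**Conclusion.** The point holds as a missing rule with a one-directional effect. As written, SAP 10.5.4 can leave a suicide death, or an attempt in a patient who attends neither ET nor Safety Follow-up, out of the behaviour and emergence counts. Its tables can then disagree with the SAE and death listings. Acts in follow-up known only from SAE reports would enter no incidence table.

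This rests on two assumptions: that the tables are filled from the C-SSRS as stated, and that the Safety Population is the denominator. The size cannot be derived from the documents beyond 0.13 percentage points per missed patient at N = 760. A reader might infer a large understatement from an assumed handful of cases, but any such fraction only restates the assumption. No test or decision rule depends on the row. What is affected is the accuracy and internal consistency of a named safety summary.

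**What to change.** In SAP 10.5.4:

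1. Keep the C-SSRS-only table. Beside it, show a combined count of patients with suicidal behaviour, and with its emergence, recorded on the C-SSRS or in an AE, SAE or death report with onset in that period. Use a pre-specified preferred-term list.
2. Fill the completed-suicide row from death and SAE data as well as the C-SSRS.
3. State the denominator, including how patients with no post-baseline C-SSRS are handled.
4. State where Safety Follow-up ends for the combined count, and which period takes an act first recorded at Visit 17.
5. Select the linked AE listing by the combined definition.

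Cost: one paragraph, a short term list and an added table column, with no new data collection. The combined count mixes two sources, which is why the C-SSRS-only count stays beside it, and it may be slightly less favourable.

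### The C-SSRS row for emergent serious ideation leaves out patients who move from level 1–3 at the lead-in baseline to level 4–5 on open-label treatment, and no other planned row isolates them

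*SAP*

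**What the plan says.** SAP Section 10.5.4 plans four rows on change in suicidality during the Open-label Treatment Period. Three concern ideation:

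- any ideation: "Emergence of suicidal ideation (no suicidal ideation at Baseline, and any type of suicidal ideation during Open-label Treatment Period";
- serious ideation, meaning level 4 or 5: "Emergence of serious suicidal ideation (no suicidal ideation at Baseline, and any serious suicidal ideation";
- worsening: "most severe suicidal ideation during Open-label Treatment Period was more severe than it was at Baseline".

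The fourth covers suicidal behavior, with none at baseline and any type later.

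The C-SSRS baseline is the last available "assessment before the first dose of study treatment during the lead-in studies", so it precedes the whole lead-in period. The protocol uses the same reference in Section 9.4.5.5.1 ("worsening of suicidal ideation (ie, compared with the first dose of study treatment from the lead-in study"). It names emergence of serious ideation without saying which baseline levels qualify, and leaves the C-SSRS details to the SAP.

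Section 10.5.4 also plans worst-level summaries by period ("The distribution of responses for the most severe suicidal ideation and most severe suicidal behavior will be presented"). Within each period "each patient will be counted only once for suicidal ideation and for suicidal behavior". Finally, "A listing of patients with suicidal ideation or suicidal behavior will be provided"; its columns are not specified. The period summaries are separate from one another, and no cross-tabulation of baseline level against worst open-label level is planned.

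**The concern.** In the any-ideation and behavior rows, emergence of something means that it was absent at baseline and present later. The serious-ideation row breaks this pattern: it requires the absence of all ideation, not only of serious ideation. A patient with a passive death wish (level 1) at the lead-in baseline who reports a plan with intent (level 5) on open-label treatment has newly serious ideation, yet is not counted.

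Safety is the primary objective and the C-SSRS is one of its measures. A reader will probably take this row as the number of patients who newly reached level 4 or 5. It can equal that number or fall below it, never exceed it. What is at stake is the meaning of this one row. The total with serious ideation on treatment is planned and is not affected.

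**Working it through.** **Inputs.** The row definitions, the baseline definition and the one-count-per-patient rule come from SAP Section 10.5.4. The documents give no figure to reproduce: there is no baseline ideation distribution and no event rate.

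**Step 1: routes.** Let level 0 be no ideation and levels 1–5 the C-SSRS ideation items.

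| Set | Routes (baseline to worst open-label) | Number |
|---|---|---|
| Worsening row | all upward moves | 5+4+3+2+1 = 15 |
| Any-ideation row | 0 to 1, 2, 3, 4, 5 | 5 |
| Level 0–3 to level 4–5 | 4 starts × 2 ends | 8 |
| Serious-ideation row | 0–4, 0–5 | 2 |
| Left out of that row | 1–4, 1–5, 2–4, 2–5, 3–4, 3–5 | 8 − 2 = 6 |

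Worsening minus any-ideation leaves 15 − 5 = 10 routes: the 6 omitted ones plus 4 others (1–2, 1–3, 2–3, 4–5). That subtraction does not isolate the omitted patients. These are counts of routes, not of patients.

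**Step 2: what the planned tables can recover.** Among patients with a baseline C-SSRS, let

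- X = patients going from level 1–3 to level 4–5 (the omitted patients),
- T = open-label level 4–5 total,
- E = the serious-ideation row,
- B = baseline level 4–5 count,
- B13 = baseline level 1–3 count,
- W = the worsening row,
- A = the any-ideation row.

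T − E equals X plus those at level 4–5 at both times, who number between 0 and B. Hence

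max(0, T − E − B) ≤ X ≤ min(T − E, W − A, B13).

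If B = 0, X = T − E exactly. Otherwise the tables may give only a range. The documents do not contain the lead-in entry criteria. The level 4/5 exclusion in this protocol applies at open-label Visit 1, so it does not make B zero.

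**Step 3: illustration.** Assumed shift tables for 760 patients (only the 760 is from the protocol), each with a true X of 4, E = 1, W − A = 45 − 32 = 13 and B13 = 119 + 37 + 7 = 163. Integer programming over all tables that match the planned outputs gave the same limits as the formula.

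| B | T | T − E | Range for X |
|---|---|---|---|
| 0 | 5 | 4 | 4 |
| 1 | 5 | 4 | 3–4 |
| 3 | 6 | 5 | 2–5 |
| 6 | 8 | 7 | 1–7 |

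**Step 4: possible size.** Let p be the share at level 1–3 among patients at level 0–3 at baseline, and RR their risk of reaching level 4–5 relative to level 0. Both are assumptions. The omitted share of newly serious cases is p·RR / (1 − p + p·RR).

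| RR | p = 5% | p = 20% | p = 40% |
|---|---|---|---|
| 0.5 | 3% | 11% | 25% |
| 1 | 5% | 20% | 40% |
| 4 | 17% | 50% | 73% |

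For example, p = 20% and RR = 4 gives 0.8 / (0.8 + 0.8) = 50%.

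**Step 5: the denominator matters too.** The SAP tabulates the row for the Safety Population and states no further denominator. With m = 1 − p + p·RR, the row percentage relative to the true level 0–3 risk is (1 − p)/m on the whole population (nobody at level 4–5 or missing at baseline) and 1/m on level-0 patients only. At p = 20% and RR = 4, m = 1.6, so the ratios are 0.8/1.6 = 0.50 and 1/1.6 = 0.63. At p = 20% and RR = 0.5, m = 0.9, and the level-0 ratio is 1/0.9 = 1.11.

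**The case against.** The strongest reply is that nothing here is an error. The row is defined in plain words, the protocol delegates the details, and the study is single-arm and descriptive with no test resting on the row. Every omitted patient is counted under worsening and once in the worst-level distribution, and appears in the listing. The planned baseline distribution will show whether B is zero, and so whether subtraction is exact. All of that stands, and it limits the weight of the point.

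A second reply is that the section has its own coherent scheme: emergence means none at baseline, and worsening takes up the rest. This is weaker. The any-ideation and behavior rows require absence of the thing that emerges; only the serious-ideation row requires absence of something broader. The SAP's laboratory criteria and ECG value criteria also start from patients below the threshold at baseline. That precedent is partial, because vital signs and the ECG change criteria do not follow it.

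Third, the proposed row would not isolate onset during open-label treatment. With the lead-in reference kept, a patient who reached level 4–5 during the lead-in period and again afterwards counts as new. One baseline assessment is also set against the worst of up to 15 scheduled on-treatment assessments. Both remarks are correct, but they apply equally to the existing rows.

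Finally, p and RR have no source in the documents. They show only that the effect could be small or large.

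**Conclusion.** The point holds as a reporting gap. The serious-ideation row covers 2 of the 8 routes from below level 4 to level 4–5. The other 6 are bounded by planned tables but not reported. Its count can only equal or understate the number of patients newly at level 4–5 relative to the lead-in baseline. The size cannot be stated from the documents; the 3% to 73% range rests wholly on the assumed p and RR. If no patient was at level 4–5 at the lead-in baseline, subtraction recovers the exact number, and the listing might do so in any case. The change should be made because safety is the primary objective and the remedy is small. The validity of the study does not depend on it.

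**What to change.** Keep the existing row and the lead-in reference. In SAP Section 10.5.4, add either a row for level 0–3 at the lead-in baseline to level 4–5 during open-label treatment, or a shift table of baseline level by worst open-label level. Base the added row's percentage on patients at level 0–3 at baseline with at least one open-label C-SSRS, and write that denominator into the SAP.

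The cost is a few lines of SAP text and one output from data already collected; the protocol text for this analysis does not change. The added count can only equal or exceed the existing row's, so the figure may look less favourable.

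A separate matter, on which this point does not rest: the protocol synopsis joins C-SSRS ideation items 4 and 5 with *and* in the Visit 1 exclusion, while Section 6.3.2 criterion 2a joins them with *or*. These are different exclusions, and the two passages must be reconciled.
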